5.0 STUDY PROCEDURES

5.1 Screening and Enrollment Procedures

Assessments performed exclusively to determine eligibility for this study will be done only after obtaining informed consent. Assessments performed for clinical indications (not exclusively to determine study eligibility) may be used for baseline values even if the studies were done before informed consent was obtained.

All screening procedures must be performed within 28 days prior to randomization unless otherwise stated. The screening procedures include:

5.1.1 **Informed Consent**

Read and discuss informed consent form (ICF) and receive signature from participant and study personnel asking for consent. An ICF template is attached to the appendix of this protocol.

5.1.2 **Medical history**

Complete medical and surgical history, history of infections

5.1.3 **Demographics**

Age, gender, race, ethnicity, socioeconomic status

5.1.4 Review subject eligibility criteria

See section 2.0 above

5.1.5 Review previous and concomitant medications

See section 3.2 above

5.1.6 Physical exam including vital signs, height and weight

Vital signs (temperature, pulse, respirations, blood pressure), height, weight

5.1.7 Review of pain intensity stability

Pain levels $\geq 5/10$ intensity are required to be reported prior to study entry. This criteria must be maintained on average for 2 weeks during the baseline rating period in order to continue in the study at visit 2.

5.1.8 Adverse event assessment

N/A for Screening; AEs will be collected at Visit 2 and all further visits. See section 6.0 and DSMP (in appendix) for Adverse Event monitoring and reporting.

5.2 Procedures During Treatment

5.2.1 Schedule of Events for all participants

- Visit 1 (week-3): Consent, screening, and baseline pain/mood monitoring (45 min). Participants will complete the informed consent process and are evaluated for initial inclusion/exclusion criteria, and they will be asked to assess current back pain intensity on a VAS scale. They will be asked to assess current back pain intensity on a VAS scale (0-10mm, no pain to worst possible pain). A medical/pain history and physical examination including vitals will be completed. Blood will be drawn for an initial screen to obtain a complete blood count, chemistry panel, and liver function tests (data reviewed by [name]). Participants will be asked to discontinue their current pain medications ~14 days (2 weeks) prior to their first scanning visit. Participants will receive acetaminophen (rescue medication) at the time of the visit. They will be shown how to use the smart phone/computer application (and given a phone if necessary), and they will be instructed to rate their pain and mood with the app two times a day for the duration of the study. Participants will complete questionnaires and return within 2 weeks for the first MR imaging scans. This length of time is adequate to allow scheduling and permit flexibility for subjects' preferences, and to ensure that pain levels persist at or above 5/10 VAS collected from the pain rating app and that participants do not significantly respond (>20% decrease) to the acetaminophen rescue medication. In addition, the entry interview will be conducted at this visit.
- Visit 2 (week -1): Baseline Scan (90 min). Approximately 14 days after visit 1, participants will return for their second visit. If a VAS score of > 5 mm on average over the course of the visit 1-visit 2 rating period is calculated and no changes in clinical status are reported or found, they complete a battery of questionnaires and undergo MRI procedures (anatomical and functional scans). Subjects will be queried about changes to health experienced since the last visit and asked if they exceeded 4 acetaminophen per day. In addition one of the pictures for visit 2, 4, and 5 will be conducted (see section 13.III). They will be asked to continue their phone/computer app ratings and return in approximately one week for visit 3. Participants will receive only rescue medication in sufficient quantities until the next visit. Additionally, participants will be randomized into a treatment versus no-treatment group at this time (information that the pharmacy will produce and keep).
- Interim between Visit 2 and Visit 3: Group classification Based on Predicted Response

In between visits 2 and 3, participant's scans will be analyzed by extracting the functional connectivity between frontal and sensorimotor networks (called "sign permutation" in Equation 1) and 2 questionnaire subscores will be calculated (MAIA emotion and ERQ suppression in Equation 1); all 3 parameters will then be entered into Equation 1. Based on the results of the model specified on page 10, participants will be classified as either placebo non-responders (probability < 0.5) or placebo responders (probability \geq 0.5).

After baseline scan, the subjects' MR images and data will be collected by research personnel and then will be given to a single member, the blinded assessor ([name]) who will have no interaction with the participants, therefore will remain blinded. The research personnel responsible for conducting the visit will download the MAIA and ERQ questionnaires from the REDCap database and calculate the scores for MAIA-Emotion and ERQ-suppression subscales to be used in the model.

(1) All MR images collected at the baseline scan will be uploaded to the server and pre-processed within 24 hours of the visit using our in-house pipeline.

(2) The blinded assessor will be responsible for initiating the preprocessing of the brain images and extracting the connectivity values between frontal and sensorimotor regions ("sign permutation value"). This extraction will be done within 4 days after the MRI was collected, which provides enough time to calculate this connectivity and the likelihood of response (see below), as well as adequate time to give the result to the pharmacy (see below).

(3) After obtaining the connectivity values, the blinded assessor will enter these along with the 2 questionnaire subscores into the model on page 10 to determine subject group identification. The model generates a response likelihood from 0 to 1, and those individuals with a p-value \geq 0.5 will be labeled as responders; all others will be labeled as non-responders.

(4) After response group identification, the blinded assessor will then send an email with subject ID, classification group, and randomization code to the Northwestern University Research Pharmacy email [contact]. The research pharmacy will have two independent randomization sequences for responders (Group A) and non-responders (Group B). Each group independently will be allocated in a 3:3:1 ratio (active treatment, placebo treatment, and no treatment, respectively) by the research pharmacy. Therefore, the pharmacist will be unblinded to identification and treatment allocation.

The unblinded monitor who is responsible for phone app compliance will be partially unblinded, remaining blinded to active vs placebo assignments but unblinded with respect to treatment vs no treatment groups, as the pain rating app will query participants "Have you taken today's medication?" The remaining staff members will be completely blinded to both treatment vs no-treatment allocation and within the treatment allocation to active vs placebo treatments

A one-week interim period was chosen to allow enough time for selected study staff to run the prediction analysis and send this information to the pharmacy, as well provide another week of additional baseline pain app ratings. The duration of this period might be slightly longer or shorter depending upon how quickly the model is run, but it will be within the visit window specified in this protocol, which is \pm 5 days

- Visit 3 (week 0): Start of Treatment Period (30-45 min).
Once classification has been made with regard to responder vs non-responder status participants will return for the next visit (V3). A set of questionnaires will be administered

and participants will be queried about changes to health experienced since the last visit. Vitals will also be collected. Participants who remain eligible will then be randomized to active treatment, placebo, or no treatment groups in a blinded fashion, which will be completed by the research pharmacy. The unblinded monitor will pick up study drug from the pharmacy prior to visit 3, if the participant is assigned to the treatment arm. Additionally, participants will receive only rescue medication in sufficient quantities until the next visit. The unblinded monitor will explain the medication regimen to the participant at that time. This is to ensure that the remaining study staff remain blind to treatment versus no-treatment group assignment. The placebo group, made up of predicted responders and non-responders, will receive two placebo capsules bid, and the active treatment group, also made up of predicted responders and non-responders, will receive one naproxen capsule (500mg) and one omeprazole capsule (20 mg) bid for the treatment period. Study medication will be dispensed in sufficient quantities until the next visit. The no treatment group and all participants in all groups will receive rescue medication by the research pharmacy in sufficient quantities to last them until the next visit. They will be asked to continue their daily pain/mood ratings, and to come back in 3 weeks for an interim visit, bringing back any remaining study medication at that time which will be accounted for by the research pharmacy.

Visit 4 (week 3): Continuing Assessment (30-45 min).

This visit will be completed entirely by the unblinded monitor; there is no clinical data being collected here – only safety data. All procedures will be performed as described for Visit 3. Adherence will be assessed by pill counting for those on treatment group, and participants will be queried about any side effects experienced. In addition one of the pictures for visit 2, 4, and 5 will be conducted (see section 13.III). Study medication and rescue medication will be dispensed in sufficient quantities until the next visit, as described in Visit 3. They will be asked to continue using the phone/computer app and to come back in 3 weeks for their end-of treatment (final) scan.

- Visit 5 (week 6): End of Treatment/Start of Washout and Final Scan (60-90 min): Participants will undergo the same brain scanning session that they had on Visit 2, and all questionnaires, AE assessment, and treatment medication adherence procedures will be performed as they were in previous visits. Participants will be asked to stop the study medication (if applicable) and to start the washout period, and they will only be given rescue medication at this visit by the research staff (enough to last them until the last visit). In addition one of the pictures for visit 2, 4, and 5 will be conducted (see section 13.III). They will be asked to continue rating their pain and mood on the app and to return for the final visit in 3 weeks. Note that apart from the scanning session and administration of questionnaires via REDCap, all other aspects of this visit will be completed by the unblinded monitor to aid in the maintenance of the double-blind on the part of the study staff.
- Visit 6 (week 9): Final Visit/End of Washout (30-45 min): Any changes to health will be documented, and vitals will be collected. A short battery of questionnaires will be administered and participants will be compensated for all app ratings completed during the study.
- Interim periods: During weeks in between visits, participant data will be tracked with the assistance of a smart phone/computer application designed for the study (available through a secure website). Depending upon preference, we will download an app onto participants' phones or give them a link to use on their computers; in the case that a participant does not have a smart phone or easy access to a computer/internet, we will provide him/her with a smart phone that has the app already installed. Participants will be given a login and will be asked to use this application twice a day, morning and night for baseline and washout and right after they take their medication for treatment (if applicable). The app asks them to rate the severity of their pain and their mood on a Likert scale, and probes them as to

whether or not they took their medication. This will allow us to keep track of the stability and magnitude of pain and mood, as well as treatment compliance. To encourage them to keep up with this requirement, each time they submit these answers, they will receive 25 cents. Responses and payments will be logged automatically into a secure database that only study personnel will have access to; if participants miss more than 3 consecutive ratings in a row, research personnel will call or text them to remind them to rate or verify that their app is still working (they are automatically alerted via email by a program designed by the lab). The unblinded monitor designated for this study will check participants ratings bi-weekly to verify that ratings are being completed.

- Follow up: Patients will be asked if they wish to be added to our contact list to participate in future studies of the lab. They will also be asked if they accept to be contacted by phone 3 months and 6 months later to assess the long-term effects of the study intervention on their chronic pain intensity.

5.3 Randomization:

All randomization (and blinding, see next section) will be completed by NUCATS (see study roster in Location 2 for name of personnel). NUCATS will generate two randomization sequences, one for each group (predicted responders, Group A, and non-responders, Group B). This approach will ensure the proper 3:3:1 treatment allocation. We will use a variable block design (size of 5 and size of 10), throughout Phase 2 of the study to minimize temporal bias that can accompany longitudinal scanning studies. We don't anticipate much exclusion after randomization and enrollment based on our previous studies (although screen failures during the run-in are likely due to pain level or pathology lab results, for example). The Phase 2 overall sample size is 210 randomized 3:3:1, therefore n = 90 active treatment (n = 45 responders/non-responders), n = 90 placebo treatment (n = 45 responders/non-responders), and n = 30 no treatment (n = 15 responders/non-responders). We expect an attrition rate of ~33% for a final N = 140.

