1.3 Predictive neural and behavioral biomarkers for clinical placebo

Summary of main findings from Phase 1 Report:

1. Using the smart phone pain ratings and within subject permutation method provides a robust method for classifying placebo responders and non-responders.
2. Three emotion-related personality outcome measures (MAIA-not worry, MAIA-emotion, ERQ-suppress) together predict future placebo response at 94% accuracy. These measures are also correlated to questionnaires regarding alternative and complementary medicine including MISS (suggestibility), HCAMQ (holistic subscale), and MLHC (health locus of control).
3. Resting state fMRI brain network information sharing between the frontal cortex and somatosensory cortex predicts placebo response at a very high accuracy.
4. Somatosensory cortex grey matter density predicts placebo response.

5. Brain white matter myelination properties do not predict placebo response.
6. Brain grey matter neurite orientation properties do not predict placebo response.
7. Limbic brain right to left asymmetry predicts placebo response.
8. The combined brain and personality final model predicts placebo response at 94% accuracy.

Conclusions from Phase 1 report:

1. The primary conclusion of these results is our ability to demonstrate that clinical placebo response is predictable from personality and from brain properties.
2. Identified personality parameters are distinct from those hypothesized in healthy subjects for experimental manipulations, and are consistent with CBP involving emotional circuitry. The relationship between these and attitudes to alternative medicine suggest common underlying mechanisms.
3. Functional information sharing results are based on a specific hypothesis we derive from our earlier similar study conducted in osteoarthritis patients, suggesting shared mechanisms of clinical placebo response predictive circuits.
4. The cortical gray matter prediction of placebo seems linked to the functional information sharing circuit and probably reflects inter-related measures.
5. The fact that we did not find a whole-brain contrast in white matter myelination properties to predict placebo response was expected and not surprising. It is possible that the white matter connectivity between the functional networks may still be distinct (remains to be tested).

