2.0 STUDY OBJECTIVES

2.1 Primary and Secondary Objectives

- 2.1.1 To evaluate the interaction between placebo response and active treatment in individuals classified as placebo responders vs non-responders. Individuals in the No Treatment group will be used as a negative control to control for regression to the mean, duration of pain, and other potential confounds.

Hypothesis: Brain functional and anatomical properties between groups after 6 weeks of treatment will identify separate circuitry for placebo analgesia and active treatment analgesia; and these groups will show distinct time courses and magnitudes of analgesia.

- 2.1.2 To test and validate brain imaging and personality parameters identified in Phase 1 that predict the propensity for placebo response and use the results to classify participants into responders vs non-responders before study intervention.

Hypothesis: Brain- and behavioral- based parameters identified as markers of placebo response in the first phase of the study will accurately predict potential responders from non-responders at first scan. The classification before study intervention will closely correspond to the responses observed at the end of treatment period.

- 2.1.3 To identify gender dependence of placebo analgesia propensity and examine brain and personality gender differences that underlie the seeming higher propensity of females for placebo response.

Hypothesis: Sexual dimorphism of the human brain and behavioral/personality differences may have a potential interaction effect and predisposition on placebo propensity. We expect to identify gender-specific biomarkers that are sexually dimorphic with regard to placebo response.

- 2.1.4 Classification of placebo responders versus non-responders for 2.1.2 will be based on Equation 1 below:

$$p = (e^{f(x)}) / (e^{f(x)} + 1)$$

$$f(x) = -3.3586 + 1.6676 * \text{Maia_Emotion} - 0.2127 * \text{Erq_Suppress} + 34.8608 * \text{sign_permutation}$$

where a probability (p) <0.5 = predicts non-responder and a probability (p) ≥0.50 predicts responder.

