5.4 Blinding Procedures

We describe this study as a 3-arm randomized controlled trial in which two treatment arms are double blinded and the third arm consists of a no-treatment group that is partially unblinded to only the unblinded monitor (who will be unblinded to treatment arm but blinded to treatment identity). Other than this person, all the remaining personnel conducting the study, collecting study endpoints, and analyzing data, including the PI, will be blind to the allocation of participants to study arm, response prediction, and treatment. All pills will be identically encapsulated to ensure blinding for study participants who receive treatment. All pills will be identical in size but there will be two colors of masking encapsulation – blue and bi-colored. This is to help the participant remember to take two different tablets (naproxen/placebo and omeprazole/placebo) at each time and thus reduce the possibility of ingesting two identical pills. The only person who will know which capsules contain active vs placebo will be the unblinded pharmacist responsible for ordering the medication, re-encapsulating the agent, filling the numbered medication vials with the appropriate drug and number of capsules, and handling drug accountability. This person will have no other involvement with study staff or be involved with any study procedures. Unmasking should not be required during the study. If allocation assignment needs to be made available, this will be done based on the circumstances outlined above. If there should be a question regarding proper allocation of treatment product, it would be possible to ascertain placebo from active drug product by opening the treatment capsules and determining if there were an enclosed tablet present. This will be prevented by sealing of all capsules prior to their being placed in treatment vials for dispensing. As mentioned above, the blinded assessor inquiring about medication compliance and adverse events will remain blinded to the treatment arm as the other study staff are, but will not be blinded to treatment versus no-treatment group assignment.

Randomization and drug allocation based on this scheme will be completed by NUCATS and Northwestern's Research Pharmacy, respectively, to ensure blinding. A pharmacist not involved in any other part of the study and without access to study data will be responsible for dispensing

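### Staff who conduct visits score two of the three Equation 1 inputs, so they hold partial information on predicted class, to which Section 5.4 says they are blind

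*Combined protocol and SAP*

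**What the plan says.** Equation 1 (Section 2.1.4) classifies each participant from MAIA-Emotion, ERQ-Suppress and a connectivity value called sign_permutation. A probability of 0.5 or more means predicted responder. All coefficients are printed.

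Section 5.2.1 divides the work between Visits 2 and 3 as follows.

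- **Questionnaire inputs.** "The research personnel responsible for conducting the visit will download the MAIA and ERQ questionnaires from the REDCap database and calculate the scores" for the two subscales used in the model.
- **Connectivity input.** "The blinded assessor will be responsible for initiating the preprocessing of the brain images and extracting the connectivity values between frontal and sensorimotor regions". This is a single person "who will have no interaction with the participants, therefore will remain blinded".
- **Running the model.** After obtaining connectivity, "the blinded assessor will enter these along with the 2 questionnaire subscores into the model on page 10 to determine subject group identification".
- **Passing on the class.** The assessor "will then send an email with subject ID, classification group, and randomization code to the Northwestern University Research Pharmacy email". No step returns the class or the connectivity value to visit staff.

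Section 5.4 says that, apart from the unblinded monitor, personnel who conduct the study, collect endpoints or analyse data "will be blind to the allocation of participants to study arm, response prediction, and treatment". It later limits the remaining staff to scanning and the online dispatch of questionnaires, with the pharmacist and the monitor as the only exceptions.

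**The concern.** The plan keeps one model input away from anyone who meets participants and hands the other two to people who do. Scoring those two inputs fits neither the blinding to response prediction nor the narrow duties that Section 5.4 describes. No reason is given for the split.

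Nothing else closes the gap. Section 9.4 restricts REDCap access to Visit 1, but the questionnaire list and the schedule table both place MAIA and ERQ at Visit 1. The three-code scheme in Section 8.2 protects analysts, not the staff who conduct visits.

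The blind matters because of what is being studied. The background section lists expectation and suggestibility among the contributors to placebo response, and pain is self-reported. A staff belief that correlates with predicted class could reach the participant and move the outcome toward the prediction. That would flatter the marker validation (2.1.2) and could disturb the class-by-treatment comparison (2.1.1). Exact knowledge of the class is not needed for this; a correlated belief is enough. The plan does not record staff belief, so an analysis could not readily separate its effect from a true class effect.

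**Working it through.** The plan states no figure for this point, so there is none to reproduce. The question is how much of the class two of the three inputs reveal.

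**Inputs from Section 2.1.4.** Intercept -3.3586; MAIA-Emotion +1.6676; ERQ-Suppress -0.2127; sign_permutation (s) +34.8608. The cut-off p ≥ 0.5 is the same as f ≥ 0.

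**Assumptions, because the documents give no score ranges.** MAIA-Emotion runs from 0 to 5. ERQ-Suppress is either an item mean (1 to 7) or a sum (4 to 28). Several ranges and SDs are tried for s, centred at zero.

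**Step 1: weight of the hidden term.** A change of 0.1 in s moves the logit by 34.8608 × 0.1 = 3.49. That equals 3.486 / 1.6676 = 2.09 MAIA points.

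**Step 2: where the class flips.** Setting f = 0 gives

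s* = (3.3586 - 1.6676 × MAIA + 0.2127 × ERQ) / 34.8608

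- MAIA 2, ERQ 4: (3.3586 - 3.3352 + 0.8508) / 34.8608 = +0.025
- MAIA 3, ERQ 4: (3.3586 - 5.0028 + 0.8508) / 34.8608 = -0.023
- MAIA 0, ERQ 7: (3.3586 + 1.4889) / 34.8608 = +0.139
- MAIA 5, ERQ 1: (3.3586 - 8.3380 + 0.2127) / 34.8608 = -0.137
- MAIA 0, ERQ 28 (sum scale, most extreme): (3.3586 + 5.9556) / 34.8608 = +0.267

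For mid-range scores, a small shift in connectivity reverses the class.

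**Step 3: share of possible score pairs for which the two scores alone settle the class.** This is the share of an even grid of score pairs with |f at s = 0| > 34.8608 × h, when s is bounded by ±h.

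| h | ERQ as mean | ERQ as sum |
|---|---|---|
| 0.05 | 58.3% | 66.9% |
| 0.1 | 16.5% | 39.8% |
| 0.2 | 0% | 6.5% |
| 0.3 | 0% | 0% |

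**Step 4: agreement of the best two-score guess with the class.** This was simulated with 400,000 draws per scale: uniform independent scores, normal s, and both the guess and the class split at their medians. The even split follows the expectation in Section 8.1.1 of about 50% responders, so chance agreement is 50%.

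| SD of s | ERQ as mean | ERQ as sum |
|---|---|---|
| 0.02 | 93.4% | 93.4% |
| 0.05 | 83.5% | 83.9% |
| 0.1 | 71.4% | 72.7% |
| 0.2 | 61.8% | 62.9% |

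The guess beats chance at every spread tried, but it comes close to the class only if connectivity hardly varies.

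**The case against.** The strongest reply is that the essential safeguard is in place. Connectivity carries the largest coefficient, it stays with someone who never meets participants, and only that person and the pharmacy are described as holding the class. A reader might infer that visit staff can work out each participant's class. The documents do not support that, as Steps 1 to 4 show.

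A reader might also infer from Section 1.3 that the hidden term adds little: "Three emotion-related personality outcome measures (MAIA-not worry, MAIA-emotion, ERQ-suppress) together predict future placebo response at 94% accuracy", and the combined brain and personality model also reached 94%. This does not follow. Both figures are accuracies for observed Phase 1 response, not agreement with the Phase 2 class. Two models of equal accuracy can classify different people differently. The questionnaire-only model also includes MAIA-not worry, which is not in Equation 1, and its coefficients are not printed. What survives is modest: the figures could lead staff to believe that the questionnaires forecast response.

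The route to bias is also narrower than it first appears. The monitor explains the regimen at Visit 3, runs Visit 4 entirely, and does everything at Visit 5 except scanning and the REDCap questionnaires. Section 5.2.1 does not say that whoever scores will conduct later visits. Pain is rated twice daily on an app between visits. Both classes are allocated 3:3:1, so a guess at class says nothing about arm, and each class has its own no-treatment group as a partial check on non-specific class effects. It would therefore go too far to say that staff behaviour could account for any class difference.

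All of this limits the size of the problem. None of it explains why contact staff do the scoring or reconciles that task with Section 5.4.

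**Conclusion.** The inconsistency is real and the exposure is partial. Staff who conduct visits score two of the three classifier inputs before treatment, under an equation printed in the protocol, while Section 5.4 promises that they are blind to response prediction and confines them to other tasks. They could guess the class better than chance but could not derive it.

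Agreement of about 62% to 93% rests on the assumed score ranges, uniform and independent scores, an even class split, and SDs of connectivity from 0.2 down to 0.02. The documents give no spread, so no single value in that range can be preferred. Correlation between connectivity and the scores would also change it.

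The size of any resulting bias in pain is unknown. A direction toward confirming the prediction is plausible but not shown. Any effect on the class-by-treatment question should be weaker than on the marker validation, because staff expectation about class could not be directed by arm. This is a worthwhile, nearly free improvement, not a flaw that undermines the trial.

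A related gap in the same text is that the assessor computes and knows every predicted class, yet the blinding statement in Section 5.4 exempts only the monitor.

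**What to change.** In Section 5.2.1, have the no-contact assessor who already receives both subscores and runs Equation 1 also export and score MAIA and ERQ. Alternatively, have REDCap score them automatically into a report that only this person can open. Remove access to the completed forms and scores from staff who conduct visits.

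In Section 5.4, state that this assessor knows the predicted class. That section also uses the title of blinded assessor for someone who asks participants about compliance and adverse events. The fix depends on the person with no participant contact described in Section 5.2.1, so the two roles should be named apart.

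The cost is a few sentences, some REDCap permission work and slightly more work for the assessor. Both questionnaires are completed at Visit 1, about two weeks before the baseline scan, so scoring need not delay classification. Visits, sample size, data collected and the model itself are unchanged.
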